This study addresses these limitations. We will collaborate with 10-12 home visiting (HV) programs serving primarily low-income women. HV is an ideal setting for this study given the large numbers of perinatal women they serve and will build on the PI's existing relationships with HV programs in Illinois. In Phase 1, we will recruit 108 pregnant women for a RCT in which half the participants will receive MB and half will receive MB with a text message enhancement (MB-TXT). MB-TXT will provide reinforcement of key MB skills that are linked to hypothesized mechanisms of change, promote completion of MB personal projects (homework), and facilitate self-monitoring of one's mood. In Phase 2, we will recruit 36 mother-father dyads for an uncontrolled pilot in which mothers will receive MB-TXT and fathers will receive a Fathers and Babies (FAB) (*previously referred to as MB DAD*) pilot curriculum developed using existing materials and data collected via qualitative research with HV clients, their partners, and HV staff.

Aim 1. To determine the feasibility and acceptability of conducting the MB-TXT intervention protocol across three HV programs in preparation for a larger fully powered RCT. Using MB text messages already developed by Co-I [name], we will collect data on home visitor adherence to delivering text messages at specified intervals, percentage of clients responding to text messages, and client comprehension of text messages as well as perceptions of text messages' utility.

Aim 2. To calculate a preliminary effect size that could be used, along with other relevant data, to calculate sample size for a future fully powered RCT.

H1. Women receiving MB-TXT will exhibit greater reductions in depressive symptoms, compared to women receiving MB.

H2. Women receiving MB-TXT will experience greater changes in hypothesized intervention mechanisms compared to women receiving MB—specifically, fewer negative cognitions and increased behavioral activation, use of social support networks, and mood regulation.

H3. Women who participate in MB-TXT will report greater completion of personal projects.

Aim 3. To develop and determine the feasibility and acceptability of a) conducting the FAB intervention protocol and b) assessing paternal and dyadic outcomes across two HV

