We will conduct a cluster RCT to determine the feasibility and acceptability of the MB-TXT intervention and calculate a preliminary effect size to determine a sample size for a future RCT. This RCT will also allow us to examine MB-TXT effects on proposed mechanisms underlying intervention efficacy. Cluster allocation by HV program minimizes contamination between study groups. We will work with 10-12 HV programs that have been trained on MB 1-on-1 and have working relationships with the PI. These programs provide a geographically, racially, and ethnically diverse set of recruitment sites. These programs are part of a network of Illinois HV programs overseen by the Illinois Governor's Office of Early Childhood Development which has supported scaling MB throughout Illinois and is enthusiastic about using text messaging to enhance intervention effectiveness. We will use a stepped wedge design—a form of RCT that involves sequential, but random, rollout of the intervention over multiple time periods. We have created two HV program clusters. Both clusters will initially implement MB 1-on-1 and will recruit MB participants for one quarter (i.e., three months) before crossing over to recruit MB-TXT participants for one quarter. MB-TXT's core curriculum is identical to MB 1-on-1 and adds a series of text messages throughout the curriculum.

Study Conditions:

MB 1-on-1. Half of our study participants (n=54) will receive MB 1-on-1. MB 1-on-1 is a manualized 12-session intervention divided into five modules. An introductory 2-session module establishes key

PROTOCOL TITLE: The Mothers and Babies Text Project

concepts related to stress, monitoring of one's mood, and ways in which one's mood influences one's internal thoughts and external environment; three 3-session modules correspond with key cognitive-behavioral elements: pleasant activities, thoughts, and social support/contact with others; a 1-session summary reviews content and identifies areas for future use of MB skills. Throughout MB, mood management skills are integrated using psycho-educational activities that encourage participants to understand connections between their mood and their activities, thoughts, and contacts with others. Content is tailored to specific needs and issues of pregnancy and the postpartum periods. Each MB session lasts 15-20 minutes and is delivered as part of a regularly scheduled home visit.

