Focus Groups: There will be six focus groups during the study. Two focus groups with HV supervisors, managers, and home visitors will take place during phase 1 and 2. Four focus groups with clients and their partners will take phase during phase 2. All focus group participants will receive \$30 remuneration in the form of a Northwestern PNC stored-value card (Visa Gift-Card).

Related to Aim 1, MB-TXT feasibility and acceptability data will be collected from clients and home visitors. Similar to previous SMS studies, we will use percentage of text responses as an indicator of "read" messages. We will assess home visitor adherence to the MB-TXT protocol by using archived data from HealthySMS to calculate percentage of texts sent at appropriate intervals, as stated in the MB Instructor Manual. Home visitors will complete a brief web-based REDCap survey after completing each MB session to assess if clients came to the session having completed their personal project. Using a 4-point Likert Scale, home visitors will also ask clients to rate the extent to which each of the 3 intersession texts was a) useful and b) easy to understand; these data will be entered into REDCap. Related to Aim 2, participant outcomes will be collected via survey at baseline and 6 months. Data will be collected and managed using REDCap electronic data capture tools hosted at Northwestern. Participants will receive \$20 remuneration for each assessment. At each assessment, a link to REDCap will be sent to study participants who can complete the assessment on any web platform (smartphone, tablet, and computer). The Project Manager or Research Assistant will complete assessments by phone for participants who prefer not to use REDCap. Depressive symptoms, as measured by the the Beck Depression Inventory-II (BDI)¹⁰⁰ a 21-item self-report measure is our primary outcome. Secondary outcomes, which map onto the hypothesized mechanisms for influence on depressive symptoms are: cognitive structuring (Experiences Questionnaire),⁸⁵ behavioral activation (Behavioral Activation Depression Scale),⁸⁶⁻⁸⁸ social support (MOS Social Support Survey),⁸⁹ and mood regulation (Negative Mood Regulation Scale).^{90,91} We estimate 15% attrition at 6months, resulting in 46 participants per arm; previous MB trials conducted by PI [name] had 12 month attrition rates <10% and we will use similar procedures for minimizing attrition.

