Analysis for Aim 2 is limited to the fact that this is a pilot study. As such, we will compare MB and MB-TXT groups at the individual level (not adjusting for potential clustering effect of either home visitor or HV program). The data will also provide key insights for future studies on how correlated the BDI scores will be over time, as longitudinal data during this postpartum period is not readily available. To address hypothesis 2, the first step in mediation is to determine the mediator's association with the criterion (group), as well as the outcome. The sample provides 80% power to detect effect sizes of 0.59 using two sided Mann Whitney tests at a type I error rate of 5% (for the between group comparison of potential mediators: negative cognitions, behavioral activation, use of support systems, mood regulation), as well as 80% power to detect correlations as small as 0.287 (comparing BDI to

PROTOCOL TITLE: The Mothers and Babies Text Project

the potential mediators). Pilot data will allow us to examine potential ranges of Intraclass Correlation Coefficients (ICC), which we need to account for in a larger RCT. These data will allow us to explore whether randomization should be done at HV program level, or the home visitor level. This sample provides 80% power to detect ICCs of 0.179 (13-14 observations at 10-12 HV programs), or of 0.261 (3 observations in 36 home visitors).

Phase 2 (FAB Development and Pilot)

Study Activities Include:

- Focus Groups with HV Clients (n=16) and their male partners (n=16)
- Development of FAB
- Pilot FAB
- Note: The research team submitted a modification to add/update details about the focus groups for phase 2 of the study. Focus group guide for these groups was submitted a modification for versions 7 of the protocol.
- Note: The research team submitted a modification to add/update details for the FAB intervention pilot in phase 2 of the study including recruitment materials. Modifications are included in version 8 of the protocol.
- FAB Post Intervention Focus Groups and Key Informant Interviews
- Note: The research team will submit a modification to add/update details about the FAB post intervention focus groups and key informant interviews. The modification will include focus and key informant consents, the focus group guide and the key informant interview guide.
-

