6.0 Incomplete Disclosure or Deception: N/A

7.0 Recruitment:

Study Participants: During phase 1, we will recruit 108 study participants from each of the participating HV programs. We will enroll 108 HV clients at 10-12 HV programs, 54 women will receive Mothers and Babies 1-on-1 without text message enhancements and 54 women will receive Mothers and Babies 1-on-1 with text message enhancements. Of the 108 women, 16 will be recruited for focus groups phase 2 of the study.

During phase 2 of the study we will conduct focus groups with the identified 16 women from the 108 group that participated in phase 1 of the study. We will also include their male partners (n=16) in two focus groups of 8 participants. Additionally we will recruit 36 women and their male partners to participate in the FAB Pilot Study.

Home Visitors: We will recruit approximately 36 home visitors from 10-12 participating HV programs throughout the state of Illinois. All HV programs recruit women at high risk for poor pregnancy and/or parenting outcomes via referrals from prenatal care clinics, community outreach, and current program participation. All of the home-visitors who are being recruited through the participating home-visiting sites have been previous trained and are currently implementing Mothers and Babies 1-on-1. Home visitors that have not been trained will receive an in-person training (see training section for more detail). Each home-visitor will identify 1-4 client that will participate in study activities, of these clients 1-2 will receive MB without Text and 1-2 will receive MB with Text. All home-visitors will implement MB without text and MB with text. Programs will initially implement MB 1-on-1 and will recruit MB participants for six months before crossing over to recruit MB-TXT participants for 6 months. To pilot FAB 1-3 home-visitors from each program will identify 1-4 client dyads that will participate in FAB pilot study activities; Home-visitors who will implement FAB will recruit dyads.

We anticipate 16 home-visitors will participate in focus groups during phase 1 and 2 of the study. 10-12 HV programs will be recruited to implement the FAB pilot.

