project. Using a 4-point Likert Scale, home visitors will also ask clients to rate the extent to which each of the 3 intersession texts was a) useful and b) easy to understand; these data will be entered into REDCap. Related to Aim 2, participant outcomes will be collected via survey at baseline, 6 months, and 9 months. Data will be collected and managed using REDCap electronic data capture tools hosted at Northwestern. Participants will receive \$20 remuneration for each assessment. At each assessment, a link to REDCap will be sent to study participants who can complete the assessment on any web platform (smartphone, tablet, computer). The Project Manager will complete assessments by phone for participants who prefer not to use REDCap. Depressive symptoms, as measured by the Beck Depression Inventory-II (BDI)¹⁰⁰ a 21-item self-report measure is our primary outcome. Secondary outcomes, which map onto the hypothesized mechanisms for influence on depressive symptoms are: cognitive structuring (Experiences Questionnaire),⁸⁵ behavioral activation (Behavioral Activation Depression Scale),⁸⁶⁻⁸⁸ social support (MOS Social Support Survey),⁸⁹ mood regulation (Negative Mood Regulation Scale), and skills utilization.^{90,91} We estimate 15% attrition at 6 months, resulting in 46 participants per arm; previous MB trials conducted by PI [name] had 12 month attrition rates <10% and we will use similar procedures for minimizing attrition.

Analysis for Aim 2 is limited to the fact that this is a pilot study. As such, we will compare MB and MB-TXT groups at the individual level (not adjusting for potential clustering effect of either home visitor or HV program). As such, the analytic sample size of 46 per arm provides > 80% power to detect effect sizes of 0.59 or 0.52 using two or one-sided (respectively) t-tests at a type I error rate of 5% for the primary outcome, the BDI.

15.0 Data Monitoring Plan to Ensure the Safety of Participants:

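### The primary BDI comparison has no defined analysis variable, standardising SD or sidedness, and the baseline BDI already collected is not used as a covariate

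*Combined protocol and SAP*

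**What the plan says.** The BDI-II is the primary outcome of Phase 1. Section 4.0 states that "participant outcomes will be collected via survey at baseline and 6 months". Section 14.0 still lists a 9-month survey as well, but the last item under Participant Outreach and Contact in Section 4.0 drops it.

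Sections 4.0 and 14.0 both describe the Aim 2 analysis in the same few words: "we will compare MB and MB-TXT groups at the individual level", without adjustment for home visitor or programme. A test for the BDI appears only in the power sentence of Section 14.0, which claims "> 80% power to detect effect sizes of 0.59 or 0.52 using two or one-sided (respectively) t-tests" with 46 per arm and a 5% type I error rate. The Mann-Whitney tests in Section 4.0 are for the potential mediators, and the correlations there relate the BDI to those mediators.

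In Section 1.0, H1 reads "Women receiving MB-TXT will exhibit greater reductions in depressive symptoms, compared to women receiving MB", and the stated purpose of Aim 2 is "To calculate a preliminary effect size that could be used, along with other relevant data, to calculate sample size" for a future trial. Section 4.0 says that the pilot will inform "how correlated the BDI scores will be over time, as longitudinal data during this postpartum period is not readily available".

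On recruitment order, Section 4.0 says "Both clusters will initially implement MB 1-on-1 and will recruit MB participants for one quarter" before crossing over to MB-TXT. Section 7.0 says that programmes "will recruit MB participants for six months before crossing over to recruit MB-TXT participants for 6 months".

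**The concern.** Four things are open for the primary comparison: the analysed variable, the SD behind the 0.59, the sidedness, and the use of baseline BDI. H1 is worded in terms of reductions, which hints at change from baseline, but a hypothesis does not define an endpoint.

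This matters because Aim 2 exists to produce an effect size. One observed mean difference gives different effect sizes depending on the SD it is divided by, and a reader planning the next trial could not tell which was used. The variable or the side could also be chosen after the data are seen.

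On precision, a 6-month t-test beats a change-score t-test when the correlation is low and loses when it is high. The plan says the correlation is not known, so it cannot tell in advance which would serve better. Adjusting for baseline removes the need to guess and uses data that will already be in hand.

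**Working it through.** **Inputs from the documents.** 54 women per arm with 15% attrition: 54 × 0.85 = 45.9, taken as 46. Type I error is 5%. Effect sizes are 0.59 (two-sided) and 0.52 (one-sided).

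**Assumptions, not in the documents.** Baseline-to-6-month correlation r = 0.3, 0.5 or 0.7; equal BDI SDs at both times; independent observations; arms comparable at baseline; two-sided 5%.

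**Step 1: the plan's own figure.** For two independent means with SD 1, the standard error is √(2/46) = 0.209 on 90 degrees of freedom. The noncentral t gives 79.9% power at 0.59 two-sided and 79.7% at 0.52 one-sided. The normal approximation gives 80.8% and 80.2%. The stated figure therefore reproduces as about 80%, and it is the power of an unadjusted two-sample test. Tested two-sided, 0.52 has only 69.4% power.

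**Step 2: variance of the estimated difference under each analysis,** in single-score SD units:

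- 6-month score: 2/46.
- Change: 2(1 − r)(2/46).
- Baseline-adjusted (ANCOVA): (1 − r²)(2/46)(1 + F/90), where F follows F(1, 90) and allows for estimating the slope; 89 degrees of freedom. The mean slope cost is 1 + 1/88 = 1.0114.

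**Step 3: power and precision when 0.59 is in single-score SDs.**

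| | r = 0.3 | r = 0.5 | r = 0.7 |
|---|---|---|---|
| Power, 6-month t-test | 79.9% | 79.9% | 79.9% |
| Power, change t-test | 65.8% | 79.9% | 95.1% |
| Power, ANCOVA | 83.1% | 89.5% | 97.4% |
| 95% half-width, 6-month | 0.41 | 0.41 | 0.41 |
| 95% half-width, change | 0.49 | 0.41 | 0.32 |
| 95% half-width, ANCOVA | 0.40 | 0.36 | 0.30 |

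A simulation of 40,000 trials per value of r agrees to within about half a percentage point.

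**Step 4: if 0.59 is in change-score SDs instead.** It then equals 0.59 × √(2(1 − r)) = 0.70, 0.59 or 0.46 single-score SDs. The change t-test has 79.9% power at every r, and ANCOVA has 93.2%, 89.5% and 85.5%.

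**Step 5: effect of the unnamed SD.** Dividing a given mean difference by the change SD rather than the single-score SD multiplies it by 1/√(2(1 − r)) = 0.85, 1.00 or 1.29.

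**Step 6: where ANCOVA loses.** It is less precise than the 6-month t-test only if |r| < √(1 − 1/1.0114) = 0.106, and than the change t-test only if r > 2/1.0114 − 1 = 0.978. In both cases the loss is at most about 1% of variance.

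**Step 7: unequal SDs.** Let k be the follow-up SD divided by the baseline SD. In follow-up SD units the change variance factor is (1 + k² − 2rk)/k². For k = 0.8 and 1.25, change-score power is 54.8% and 73.9% at r = 0.3, 68.6% and 86.3% at r = 0.5, and 87.4% and 97.3% at r = 0.7. The other two analyses do not move.

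**Step 8: true baseline gap between arms.** For a gap g, the ANCOVA and change estimates differ by g(1 − r). With g = 0.2 SD this is 0.14, 0.10 or 0.06 SD.

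**The case against.** The strongest reply is that this is a pilot, and says so. Its effect size is called preliminary and is to be used with other data. If means, SDs and the correlation are all reported, a later planner can convert one effect size into another. That is fair, and it limits the harm, but the plan does not commit to that reporting. The risk of an unlabelled effect size or a choice made after the fact remains.

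Second, the covariate is unmentioned rather than ruled out, and a change-score analysis would already use the baseline. Both are true. They narrow the ambiguity without closing it.

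Third, preferring ANCOVA rests on arms comparable at baseline. Here each programme recruits MB women before MB-TXT women. If the cohorts' true baselines differ, ANCOVA and change scores estimate different quantities and the data do not show which is right. This stands, and it is why a change-score sensitivity analysis belongs in the fix. It also makes it more important to choose in advance. Some calendar overlap between arms is possible if the two clusters cross over at different times, since Section 4.0 also describes a sequential random rollout.

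Fourth, the power gains depend on an assumed correlation and ignore clustering. They are illustrative, and at r = 0.3 the gain over a 6-month t-test is only about 3 points.

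Finally, the leftover 9-month survey in Section 14.0 is settled by Section 4.0 in favour of 6 months. Section 4.0 does use both 6 months and 6 months post-intervention, so the endpoint sentence should say what the 6 months are counted from.

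**Conclusion.** The concern holds. The power arithmetic is sound for an unadjusted t-test; the gap lies in the analysis it is meant to describe. No section names the analysed variable, the standardising SD, one sidedness or a baseline covariate for the primary comparison.

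Under the stated assumptions, baseline adjustment is at least as precise as either t-test for any r between about 0.11 and 0.98. The gain is small at low correlation and substantial at moderate or high correlation. The change in effect size from the choice of SD, by a factor of 0.85 to 1.29, bears directly on Aim 2. The point does not invalidate the pilot, but it should be put right because it affects the trial's main quantitative output. Baseline adjustment removes neither calendar-period confounding nor clustering.

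**What to change.** State one primary analysis: 6-month BDI regressed on arm with baseline BDI as covariate, two-sided at 5%, within whatever model is adopted for clustering and period. Report the adjusted mean difference with a 95% interval, and an effect size with its standardising SD named, for example the pooled baseline SD. Report baseline BDI mean and SD by arm. Give the change-score estimate as a sensitivity analysis, because the arms are recruited in succession.

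Keep the two-sided 0.59 as the unadjusted power statement, worded as about 80%, and drop the one-sided 0.52. Remove the 9-month survey from Section 14.0.

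The cost is two or three sentences of analysis wording and one degree of freedom. No new data are needed.
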